4.3 Sample Size

There is no sample size calculation for the Maintenance study.

4.4 Interim Analysis

No interim analysis is planned for the Maintenance study.

5.0 Analysis Populations

5.1 Definition for Analysis Populations

The following populations will be used for analyses in the study:

Modified Intent-to-Treat (mITT) set includes all ITT subjects who achieve clinical response (CR-70) at Week 12. The mITT set is the primary population for the efficacy analysis for the Maintenance Study.

The safety set consists of all subjects who received at least one injection of study drug during maintenance study. The safety set will be analyzed as treated, according to treatment the subject actually received. The safety set will be used only for safety analysis.

5.2 Variables Used for Stratification of Re-Randomization

At Week 12, subjects are re-randomized in a 1:1 ratio to one of two double-blinded exploratory treatment regimens (clinically adjusted [CA] regimen and adalimumab therapeutic drug monitoring [TDM] regimen). The re-randomization at Week 12 is stratified by induction treatment regimen, clinical response (CR-70) status at Week 12, and decrease in SES-CD > 50% from Baseline per the site investigator reading at Week 12. Among subjects achieving decrease in SES-CD > 50% from Baseline at Week 12, the randomization is further stratified by achievement of an SES-CD ≤ 4 and at least a 2 point reduction versus baseline and no subscore greater than 1 in any individual variable using the Week 12 SES-CD value provided by the site.

The randomization schedule was prepared by the Statistics Department of AbbVie.

6.0 Analysis Conventions

Definition of Induction Baseline

The Induction Baseline visit date is the date when the first dose of study drug is received and referred to as Day 1 or Week 0. If a subject has not taken any study drug during Induction Study, the randomization date will be used as Day 1. The Baseline value for a variable is defined as the last non-missing value on or before the date of the first dose of study drug.

Definition of Maintenance Baseline

The Maintenance Baseline visit date is the date when the first dose of study drug during Maintenance Study is received and referred to as Day 1 of Maintenance Study or Week 0 of Maintenance Study. If a subject has not taken any study drug during Maintenance Study, the re-randomization date will be used as Day 1. The Maintenance Baseline value for a variable is defined as the last non-missing value on or before Day 1 of Maintenance Study, and after the Induction Baseline.

Definition of Maintenance Final Observation

Final Observation in the 56-week period (44-week double-blind Maintenance Study) is defined as the last non-missing observation collected within 70 days following the last dose of study drug who are re randomized.

Definition of Rx Days (Days Relative to the First Dose of Maintenance Study Drug)

Rx Days are calculated for each time point of interest and it provides a quantitative measure of days between the event and the first dose date. That is, the Rx Day is calculated as the event date minus the date of first dose of study drug plus 1. The Rx Day will be a negative value when the time point of interest is prior to the date of first dose of study drug, and the Rx Day will be a positive value when the time point of interest is after

the first dose date. By this calculation algorithm the first dose day is Rx Day 1 of Maintenance Study, while the day prior to the date of first dose is defined as Rx Day –1 of Maintenance Study (there is no Rx Day 0). Rx Days are used to map actual study visits to the protocol specified study visits.

Dealing with Multiple Measurements Collected on the Same Day

For efficacy related analyses, if multiple measurements for a particular parameter are collected on the same day for the same subject, the average of those measurements will be used.

For safety related analyses, if multiple measurements are made for a particular laboratory or vital sign parameter on the same day for the same subjects, the one with later time will be used if collection time is also available, or the average of the values will be used in the analyses of change from Baseline. For summaries and listings for shift from baseline and potentially significant values, all collected values within the pre-specified treatment window will be used.

Definition of Analysis Windows

Since subjects do not always adhere to the study visit schedule, the following rules will be applied to assign actual visits to protocol-specified visits including early termination visits. For each study visit mentioned in the protocol, a nominal or target day will be selected to represent the corresponding visit along with a window around the target day. Windows will be selected in a non-overlapping fashion so that a date collected on the CRF does not correspond to multiple visit windows. Moreover, windows will not discard any Post-Baseline measurement recorded on the CRF. If a subject had two or more actual visits in one visit window, the visit closest to the schedule visit will be used as the study visit for that window. If two visits are equidistant from the target, then the later visit will be used for reporting. If more than one assessment is collected on the same day, then the average of those assessments will be used in analyses.

Table 3. Visit Windows for Analysis of CDAI and Vital Signs for Maintenance Study

Scheduled Week	Nominal Day	Time Window (Rx Day Range)
Week 12 (Week 0 of Maintenance Study)	1 ^a	≤ 1
Week 14 (Week 2 of Maintenance Study)	15	2 – 36
Week 20 (Week 8 of Maintenance Study)	57	37 – 78
Week 26 (Week 14 of Maintenance Study)	99	79 – 106
Week 28 (Week 16 of Maintenance Study)	113	107 – 134
Week 34 (Week 22 of Maintenance Study)	155	135 – 176
Week 40 (Week 28 of Maintenance Study)	197	177 – 204
Week 42 (Week 30 of Maintenance Study)	211	205 – 232
Week 48 (Week 36 of Maintenance Study)	253	233 – 281
Week 56 (Week 44 of Maintenance Study)	309	282 – 379

Rx Day = date of visit – date of first study drug injection in double-blind maintenance study + 1

- a. Day of first dose of study drug in double-blind maintenance study. If a subject has not taken any study drug during Maintenance Study, the randomization date will be use as Day 1 of Maintenance Study.

Table 4. Visit Windows for Analysis of Chemistry, Hematology, Urinalysis, hs-CRP, Fecal Calprotectin, Abdominal Pain Rating Scale, IBDQ, EQ-5D, and WPAI for Maintenance Study

Scheduled Week	Nominal Day	Time Window (Rx Day Range)
Week 12 (Week 0 of Maintenance Study)	1 ^a	≤ 1
Week 26 (Week 14 of Maintenance Study)	99	2 – 148
Week 40 (Week 28 of Maintenance Study)	197	149 – 253
Week 56 (Week 44 of Maintenance Study)	309	254 – 379

Rx Day = date of visit – date of first study drug injection in double-blind maintenance study + 1

- a. Day of first dose of study drug in double-blind maintenance study. If a subject has not taken any study drug during Maintenance Study, the randomization date will be use as Day 1 of Maintenance Study.

Table 5. Visit Windows for Analysis of SES-CD for Maintenance Study

Scheduled Week	Nominal Day	Time Window (Rx Day Range)
Week 12 (Week 0 of Maintenance Study)	1 ^a	≤ 1
Week 56 (Week 44 of Maintenance Study)	309	2 – 379

Rx Day = date of visit – date of first study drug injection in double-blind maintenance study + 1

- a. Day of first dose of study drug in double-blind maintenance study. If a subject has not taken any study drug during Maintenance Study, the randomization date will be use as Day 1 of Maintenance Study.

Table 6. Visit Windows for Analysis of Fistulas and EIM for Maintenance Study

Scheduled Week	Nominal Day	Time Window (Rx Day Range)
Week 12 (Week 0 of Maintenance Study)	1 ^a	≤ 1
Week 56 (Week 44 of Maintenance Study)	309	2 – 379

Rx Day = date of visit – date of first study drug injection in double-blind maintenance study + 1

- a. Day of first dose of study drug in double-blind maintenance study. If a subject has not taken any study drug during Maintenance Study, the randomization date will be use as Day 1 of Maintenance Study.

CD-Related Concomitant Corticosteroid Therapy

Subjects in whom the CD-related corticosteroids (systemic or rectal corticosteroids) that were not being taken at Induction Baseline and are initiated during the study or who have equivalent dose of these medications increased to greater than the dose taken at Induction Baseline will be censored for efficacy assessments (i.e., will be considered non-responders for categorical endpoints and will have last non-missing values carried forward for non-categorical assessments) from that point through the end of the study. These subjects will continue to be evaluated in the safety population.

Subjects in whom systemic corticosteroids were used at Induction Baseline and initiated rectal corticosteroids during the study will be censored for efficacy assessment, regardless of rectal corticosteroid dose.

The equivalent steroid dose will be determined based on the table below:

Corticosteroid	Equivalent Dose (mg)
Cortisone	25
Hydrocortisone	20
Prednisone	5
Prednisolone	5
Triamcinolone	4.0
Methylprednisolone	4.0
Betamethasone	0.75
Dexamethasone	0.75
Budesonide	1
Beclomethasone	5
Beclometasone	5

Definition of Missing Data Imputation

The following imputation methods will be used to impute missing values in the efficacy analyses. In addition, an observed case analysis will be performed.

Non-Responder Imputation (NRI)

The NRI approach is used for binary efficacy variables. These variables can take values of 'Achieved' or 'Not Achieved' or may be missing for any reason including discontinuation from study. According to the NRI imputation approach, all missing values will be considered as 'Not Achieved.'

Last Observation Carried Forward (LOCF)

For all variables (categorical variables and continuous variables), the following rules will be used for the LOCF approach:

1. Maintenance Baseline and Pre-Maintenance Baseline values will not be used to impute the missing Post-Maintenance Baseline values.

2. Missing values after Study Day 1 will be imputed using the latest non-missing values after Day 1 and prior to the missing value. If there are no non-missing values after Maintenance Baseline, then the LOCF value will be missing.

Mixed-Effect Model Repeated Measure (MMRM)

The MMRM model will be used for continuous efficacy variables with longitudinal data as a sensitivity analysis. The MMRM model includes the Induction baseline values as covariate; randomization strata, region (US versus non-US), treatment, time point and treatment-by-time point interaction as fixed effects; and subjects within treatment as random effect. An unstructured (co)variance structure will be used to model the within-subject error. The comparison at a time point will be the contrast between treatments at that time point.

Observed Case (OC)

Observed case analysis will be performed such that missing values will not be imputed. Subjects in whom the following CD-related systemic or rectal corticosteroids that were not being taken at Induction Baseline and are initiated during the study or who have dosages of these medications increased to greater than the dose taken at Induction Baseline will be censored for efficacy assessments (i.e., will be considered non-responders for categorical endpoints and the observed non-categorical assessments will be replaced by last non-missing values prior to censoring) from that point through the end of the study.

Subjects in whom systemic corticosteroids were used at Induction Baseline and initiated rectal corticosteroids during the study will be censored for efficacy assessment, regardless of rectal corticosteroid dose.

Imputation of Missing Dates

For Baseline, efficacy, and safety parameters, if the day and/or month are missing, the following conventions will be used to impute the missing dates:

- 01 for missing start day
- End of month for missing end day
- January 1st for missing start month
- December 31st for missing end month

Rule for CDAI Calculation

Up to 14 days of diary entries will be evaluated from the ePRO tool for the CDAI calculation for each visit. The diary entries on the days the subjects receive endoscopy preparation medications, the day of endoscopy procedure, and 2 days after endoscopy procedure will be excluded. For each CDAI subscore, the available scores from the most recent diary days (at least 4 days, up to 7 days) prior to actual day of the study visit will be summed, and then multiplied by the corresponding multiplier to get subtotal score. If available diary entries are fewer than 7 days, the subtotal score will be calculated as (summed total available score/number of days) \times 7 \times corresponding multiplier. The three subtotal scores that are based on ePRO (number of liquid/very soft stools, abdominal pain rating, and general well-being) will then be rounded to one decimal. The final CDAI is rounded to a whole number.

If a subject has less than 4 days of diary data, the total CDAI score will not be calculated and will be considered missing.

Sensitivity analyses will be performed to make use of all available data based on the above rule if more than 5% of subjects have less than 4 days of diary data.

Definition of Clinical Remission

CDAI < 150.

Definition of Clinical Response

Decrease in CDAI \geq 70 points from Induction Baseline.

Definition of Enhanced Clinical Response

Decrease in CDAI \geq 100 points from Induction Baseline.

Definition of Endoscopic Remission

Simplified Endoscopic Score for Crohn's Disease (SES-CD) \leq 4 and at least 2 point reduction versus Induction baseline and no subscore greater than 1 in any individual variable, as scored by central reviewer.

Definition of Endoscopic Response

Decrease in SES-CD $>$ 50% from Induction Baseline (or for a Induction Baseline SES-CD of 4, at least a 2 point reduction from Induction Baseline), as scored by central reviewer.

Stool Frequency + Abdominal Pain Score (SFPS)

SFPS is the CDAI components "Number of liquid or very soft stools" and "Abdominal pain" (Stool [liquid/soft] Frequency + Abdominal Pain Score). The sub-total score for each component is calculated as the sum of the 7 day diary score multiplied by the corresponding multiplier.

Definition of Time to Dose Escalation

Time to Dose Escalation is defined as number of days from Study Day 1 in Maintenance Study to the date of Dose Escalation. It is calculated as (date of dose escalation – Study Day 1 date in Maintenance Study). Subjects who discontinue prior to dose escalation are censored at the time of discontinuation. Subjects who are not experiencing dose escalation by Week 56 are censored at the Week 56 visit.

Definition of Symptomatic Remission

Average daily stool frequency ≤ 2.8 (and not worse than induction baseline) and average daily abdominal pain ≤ 1.0 (and not worse than induction baseline). The analysis will be only performed on subjects with induction baseline average daily stool frequency score ≥ 4.0 or average daily abdominal pain score ≥ 2.0 .

Definition of Symptomatic Response

Average daily stool frequency at least 30% reduction from induction baseline and average daily abdominal pain not worse than induction baseline or average daily abdominal pain at least 30% reduction from induction baseline and average daily stool frequency not worse than induction baseline. The analysis will be only performed on subjects with induction baseline average daily stool frequency score ≥ 4.0 or average daily abdominal pain score ≥ 2.0 .

Discontinued Corticosteroid Use at Each Visit during Maintenance Study Among Subjects Who Used Corticosteroids at Induction Baseline

Discontinued steroid use at each visit is based on the steroid use on the date of CDAI measurement for that visit. If the subject has no CDAI for the visit, the date of vital signs will be used. If no vital signs date, then the steroid use on the nominal day for that visit will be evaluated.

If a subject discontinued the study, 'discontinued corticosteroid use' will be classified as No from that point through the end of the study.

If a subject met censoring criteria for CD-related concomitant therapy, 'discontinued steroid use' will be classified as No from that point through the end of the study.

SES-CD Scoring

All videotaped colonoscopies will undergo central review providing the investigator's SES-CD score meets the entry criteria. Two primary central reviewers will evaluate the

videotaped colonoscopies separately and provide their SES-CD scores to Parexel. A third central reviewer will adjudicate between the two initial reviewers' SES-CD scores if there is discrepancy in any SES-CD variable. The adjudicator will select the final SES-CD score that he/she most agrees with from those provided by the two primary reviewers, and this final SES-CD score will be entered into the study database and be used for the study's efficacy analyses. If there is no discrepancy between the two primary central reviewers, that score will be entered into the study database and serve as the SES-CD score to be used for the study's efficacy analyses.

If there is a missing SES-CD individual variable in the SES-CD that serves as the SES-CD for the study's efficacy analyses, the following imputation rules will be applied:

The missing SES-CD individual variables at Baseline will be imputed as 0. The Week 12 or Week 56 missing SES-CD individual variables will be imputed as 0 if there are 8 or fewer missing individual variables. If more than 8 individual variables are missing, the total SES-CD will be missing for that visit.

Bristol Stool Chart Score

Up to 14 days of diary entries will be evaluated from the ePRO tool for the Bristol Stool Chart calculation. These assessments on the day of endoscopy procedure, the day before endoscopy procedure (due to preparation medications), and 2 days after endoscopy procedure are excluded. The 7 most recent non-missing assessments will be used for the analysis. Bristol Stool Form Scale is not a continuous variable. The new variable Bristol Stool Chart score is defined as the number of days the subjects with Type 6 or Type 7 divided by the total number days with non-missing assessments, rounded to two decimals.

If a subject has less than 4 days of diary data, the Bristol Stool Chart score will not be calculated and will be considered missing.

If a subject achieved reduction from Baseline $\geq 50\%$, this subject will be classified as Bristol Stool Chart Responder.

Hs-CRP

From November 2014 to December 2015, Roche hs-CRP kit lot 604450 was in use at ICON. In December 2015 ICON altered the study team of a bias in the lot of the Roche Diagnostic C-reative protein high sensitive reagent. ICON then informed the study team of the extent of the under recovery in March 2016. This lot was "retrospectively expired" as the low standard beads agglutinated causing specimen results that are below 5 mg/L to be up to 25% lower than the accurate value. ICON later determined with Roche that the affected samples were those tested from May 18, 2015 to December 2015.

In the Study M14-115 approximately 423 samples were affected according to ICON. AbbVie obtained the final listing of affected samples/results from ICON on August 10, 2016. A correction factor developed by Roche and ICON will be applied to all affected specimens with a concentration between 0.51 to 4.99 mg/L and will replace the initially provided hs-CRP values in the study database.

For Study M14-115, both Roche and Abbott platform are used to measure hs-CRP. The study team has decided to use Abbott platform for CSR analysis. If hs-CRP was measured by Roche platform only, the value will be converted to Abbott equivalent by a conversion factor.

EuroQol-5D-5L (EQ-5D)

EQ-5D is a standardized measure of health status developed by the EuroQol Group in order to provide a simple, generic measure of health for clinical and economic appraisal. The EQ-5D consists of 2 pages. The first page measures 5 dimensions of the health status (mobility, self-care, usual activities, pain/discomfort, and anxiety/depression) with 5 levels per dimension (no problems, slight problems, moderate problems, severe problems, and unable corresponding to Level 1 to Level 5 respectively). The second page is an EQ Visual Analogue Scale (EQ VAS). EQ-5D health states, defined by the EQ-5D-5L descriptive system on the first page, may be converted into a single index

value. The change from baseline of the index value and EQ VAS will be analyzed and reported. UK scoring algorithm will be used (Table 7).

Table 7. An EQ-5D-5L Value Set for England

	Central Estimate	Value for Health State 23245
Mobility		
No Problem	0	
Slight	0.051	0.051
Moderate	0.063	
Severe	0.212	
Unable	0.275	
Self-Care		
No Problem	0	
Slight	0.057	
Moderate	0.076	0.076
Severe	0.181	
Unable	0.217	
Usual Activities		
No Problem	0	
Slight	0.051	0.051
Moderate	0.067	
Severe	0.174	
Unable	0.190	
Pain/Discomfort		
No	0	
Slight	0.060	
Moderate	0.075	
Severe	0.276	0.276
Unable	0.341	
Anxiety/Depression		
Not	0	
Slight	0.079	
Moderate	0.104	
Severe	0.296	
Unable	0.301	0.301
The value for health state 23245: $1 - 0.9675 \times (\text{sum of the subscores})$		$1 - 0.9675 \times (0.051 + 0.076 + 0.051 + 0.276 + 0.301) = 0.270$

The index value is $1 - 0.9675 \times \text{sum of 5 components based on central estimates}$.

The minimum index value is -0.281 (health state 55555), and the maximum index value is 1 (health state 11111).¹

If one of the 5 dimensions is missing, the EQ-5D index value will be missing.

7.0 Demographics, Baseline Characteristics, Medical History, and Previous/Concomitant Medications

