- a. For subjects experiencing an active infection or those for whom the investigator feels dose escalation is not advisable, the investigator should contact the Study Designated Physician.
- b. Measured from the serum concentration taken at the prior study visit.
- c. Measured using hematocrit taken from prior study visit for CDAI calculation.
- d. Measure using hs-CRP from the prior or current study visit.

A schematic of the study design is presented in [Figure 2](#).

Figure 2. Study Schematic

Clinical evaluation is included at the following visits: Baseline, Weeks 2, 4, 6, 8, 12, 14, 20, 26, 28, 34, 40, 42, 48, and 56/PD. An electronic diary is dispensed at the Screening visit. In addition to routine physical examination, CDAI calculation, diary review, laboratory, adverse event, concomitant medication and vital sign assessments, the following are collected:

- Results of study questionnaires (inflammatory bowel disease questionnaire [IBDQ], European Quality of Life 5 dimensions [EQ-5D], work productivity and impairment [WPAI]) at Baseline, Week 4, Week 8, Week 12, Week 26, Week 40 and Week 56/PD.
- Calculation of the SFPS at Baseline, Week 2, Week 4, Week 6, Week 8, Week 12, Week 14, Week 20, Week 26, Week 28, Week 34, Week 40, Week 42, Week 48 and Week 56/PD. The Screening results serve as the Baseline value.
- Results of daily Bristol Stool Form Scale beginning at Baseline through Week 56/PD.
- Results of 11-point Abdominal Pain Rating Scale beginning at Baseline, Week 2, Week 4, Week 6, Week 8, Week 12, Week 26, Week 40, and Week 56/PD.
- Serum for measurement of adalimumab concentrations just prior to dosing at Baseline, Week 2, Week 4, Week 6, Week 8, Week 12, Week 26, Week 40, and Week 56/PD.
- Serum for measurement of Anti-Adalimumab Antibodies (AAA) just prior to dosing at Baseline, Week 4, Week 12, Week 26, Week 40, and Week 56/PD.
- Serum for measurement of infliximab serum levels and Human Anti-Chimeric Antibodies (HACA) just prior to dosing at Baseline.
- Serological biomarkers/mRNA at Baseline, Week 2, Week 4, Week 8, Week 12, Week 26, Week 40, and Week 56/PD.
- Stool samples for analysis of fecal calprotectin during Screening, at Week 4, Week 12, Week 26, and Week 56/PD.

- Stool samples for microbiota metagenomic analyses during Screening, at Week 4, Week 12, Week 26, and Week 56/PD. The stool samples should be taken before starting bowel preparations for endoscopy.

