10.2 Efficacy Analyses

This section provides the details of the efficacy analysis for the Maintenance Study.

For these endpoints which are categorical variables, NRI method of imputation will be used for the missing values. LOCF will be used as a sensitivity analysis wherever applicable.

Both LOCF and OC analyses will be performed for continuous endpoints. The LOCF analysis is considered primary for inferential purposes. In addition, Mixed-Effect Model Repeated Measure (MMRM) will be applied as a sensitivity analysis, wherever appropriate, for the longitudinal continuous endpoints.

For endoscopy related endpoints, there will be no LOCF imputation as there is only one post-baseline endoscopy during Maintenance. OC will be used as a sensitivity analysis.

The difference in proportions of subjects between treatment groups will be analyzed using the two-sided Cochran-Mantel-Haenszel (CMH) test adjusted for induction treatment regimen, and decrease in SES-CD > 50% from Induction Baseline per central reading at Week 12. Additionally, the CMH-based two-sided 95% confidence interval (CI) for the difference in the proportions between the treatment groups will be calculated.

The difference in change from Induction Baseline between treatment groups will be analyzed using an ANCOVA model including factors of treatment, induction treatment regimen, decrease in SES-CD > 50% from Induction Baseline per central reading at Week 12 and Induction Baseline values. Parameter estimates with 95% confidence interval and *P*-value will be provided.

All efficacy endpoints for Maintenance Study are non-ranked.

- Proportion of subjects who achieve endoscopic response (SES-CD > 50% from Induction Baseline [or for a Induction Baseline SES-CD of 4, at least a 2 point

reduction from Induction Baseline]) at Week 56 among subjects with endoscopic response at Week 12

- Proportion of subjects who achieve endoscopic remission ($\text{SES-CD} \leq 4$ and at least a 2 point reduction versus Induction Baseline and no subscore greater than 1 in any individual variable) at Week 56 among subjects with endoscopic remission at Week 12.
- Proportion of subjects who achieve endoscopic remission ($\text{SES-CD} \leq 4$ and at least a 2 point reduction versus Induction Baseline and no subscore greater than 1 in any individual variable) at Week 56 among subjects with endoscopic response at Week 12.

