- Proportion of subjects with enhanced clinical response (decrease CDAI \geq 100 points from Induction Baseline) at each scheduled visit in Maintenance Study.
- Proportion of subjects who discontinue corticosteroid use at each scheduled visit in Maintenance Study among subjects taking corticosteroid at Induction Baseline.
- Proportion of subjects who achieve a composite subtotal score of SFPS < 50 at Week 56 who had an SFPS \geq 100 at Induction Baseline.
- Proportion of subjects who achieve SES-CD \leq 3 and at least a 2 point reduction versus Induction Baseline and no subscore greater than 1 in any individual variable at Week 56.
- Proportion of subjects with SES-CD = 0 at Week 56.
- Change from Induction Baseline in fecal calprotectin level at each scheduled visit in Maintenance Study.
- Change from Induction Baseline in hs-CRP at each scheduled visit in Maintenance Study.

- Change in IBDQ total score and individual IBDQ domain scores (bowel, emotional, social, systemic) from Induction Baseline at each scheduled visit in Maintenance Study.
- Change in WPAI from Induction Baseline at each scheduled visit in Maintenance Study.
- Change in EQ-5D from Induction Baseline at each scheduled visit in Maintenance Study.
- Change in CDAI from Induction Baseline at each scheduled visit in Maintenance Study.
- Change in SFPS from Induction Baseline at each scheduled visit in Maintenance Study.
- Change in Abdominal Pain Rating Scale score from Induction Baseline at each scheduled visit in Maintenance Study.
- Change in Bristol Stool Chart score from Induction Baseline at each scheduled visit in Maintenance Study.
- Proportion of subjects who achieve CDAI remission ($CDAI < 150$) at each scheduled visit in Maintenance Study.
- Proportion of subjects who achieve SFPS remission ($SFPS < 50$) at each scheduled visit in Maintenance Study.
- Proportion of subjects with major CD related event (e.g., hospitalization, bowel surgery, abscess drainage) in Maintenance Study.
- Proportion of subjects with no draining fistulas at Week 56 among subjects with draining fistula at Induction Baseline.
- Proportion of subjects in each treatment group with $> 50\%$ reduction from Induction Baseline in the number of draining fistulas at Week 56 among subjects with draining fistula at Induction Baseline.
- Resolution of extra-intestinal manifestations at each scheduled visit in Maintenance Study.

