- a. Day of first dose of study drug in double-blind induction study. If a subject has not taken any study drug during Induction Study, the randomization date will be use as Day 1.
- b. Rx Day 98, or first dose of maintenance, or first dose of study drug in Study M14-347, whichever earlier.

Table 4. Visit Windows for Analysis of Chemistry and Hematology for Induction Study

Scheduled Week	Nominal Day	Time Window (Rx Day Range)
Week 0	1 ^a	≤ 1
Week 2	15	2 - 22
Week 4	29	23 – 43
Week 8	57	44 – 71
Week 12	85	72 – 98 ^b

Rx Day = date of visit – date of first study drug injection in double-blind induction study + 1

- a. Day of first dose of study drug in double-blind induction study. If a subject has not taken any study drug during Induction Study, the randomization date will be use as Day 1.
- b. Rx Day 98, or first dose of maintenance, or first dose of study drug in Study M14-347, whichever earlier.

Table 5. Visit Windows for Analysis of SES-CD, Fistulas, and EIM for Induction Study

Scheduled Week	Nominal Day	Time Window (Rx Day Range)
Week 0	1 ^a	≤ 1
Week 12	85	2 – 168 ^b

Rx Day = date of visit – date of first study drug injection in double-blind induction study + 1

- a. Day of first dose of study drug in double-blind induction study. If a subject has not taken any study drug during Induction Study, the randomization date will be use as Day 1.
- b. Rx Day 168, or first dose of maintenance + 7 days, or first dose of study drug in Study M14-347 + 7 days, whichever earlier. No + 7 days for Fistulas and EIM.

Table 6. Visit Windows for Analysis of Fecal Calprotectin for Induction Study

Scheduled Week	Nominal Day	Time Window (Rx Day Range)
Week 0	1 ^a	≤ 1
Week 4	29	2 – 57
Week 12	85	58 – 112 ^b

Rx Day = date of visit – date of first study drug injection in double-blind induction study + 1

- a. Day of first dose of study drug in double-blind induction study. If a subject has not taken any study drug during Induction Study, the randomization date will be use as Day 1.
- b. Rx Day 112, or first dose of maintenance, or first dose of study drug in Study M14-347, whichever earlier.

CD-Related Concomitant Corticosteroid Therapy

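### Maintenance SAP Table 4 gives fecal calprotectin a Week 40 analysis visit, but no stool sample is scheduled at Week 40

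*SAP*

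**What the plan says.** **Sampling.** Maintenance SAP section 4.2 lists "Stool samples for analysis of fecal calprotectin during Screening, at Week 4, Week 12, Week 26, and Week 56/PD". Protocol sections 1.2 and 5.1 give the same times. In maintenance that means Week 26 and Week 56/PD, with nothing at Week 40.

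**Windows.** Maintenance SAP section 6.0, Table 4, covers chemistry, hematology and urinalysis together with "hs-CRP, Fecal Calprotectin, Abdominal Pain Rating Scale, IBDQ, EQ-5D, and WPAI for Maintenance Study". Its rows are Week 26 (nominal Day 99, Days 2-148), Week 40 (Day 197, Days 149-253) and Week 56 (Day 309, Days 254-379). The first column is headed as the scheduled week, and the middle row begins "Week 40 (Week 28 of Maintenance Study".

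**Mapping.** Section 6.0 states that "the following rules will be applied to assign actual visits to protocol-specified visits including early termination visits" and that "windows will not discard any Post-Baseline measurement recorded on the CRF". If two visits share a window, the one closest to schedule is used.

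**Analysis.** Section 10.2 lists "Change from Induction Baseline in fecal calprotectin level at each scheduled visit in Maintenance Study". For continuous endpoints it plans LOCF and OC analyses, with MMRM as a sensitivity analysis where appropriate, and says: "The LOCF analysis is considered primary for inferential purposes".

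**Comparison.** The Induction SAP gives calprotectin a table of its own, "Table 6. Visit Windows for Analysis of Fecal Calprotectin for Induction Study", with rows for Baseline and the two sampled visits (Weeks 4 and 12) only.

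**The concern.** Calprotectin shares a window table with variables that do have a Week 40 visit, and so acquires a Week 40 row. A programmer who follows Table 4 together with the by-visit endpoint would produce a comparison of the clinically adjusted and therapeutic drug monitoring regimens at Week 40, with a confidence interval and p-value, although no sample was scheduled there.

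The observed part of that comparison would be selected on discontinuation, which happens after re-randomisation. The carried-forward part would largely repeat the Week 26 contrast under a later label, so a reader could take it as separate evidence that an effect lasts.

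**Working it through.** **1. Reproduce Table 4.** Nominal day = (study week - 12) x 7 + 1.
- Week 26: 14 x 7 + 1 = 99
- Week 40: 28 x 7 + 1 = 197
- Week 56: 44 x 7 + 1 = 309

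Boundaries are midpoints: (99 + 197)/2 = 148 and (197 + 309)/2 = 253. The last bound is 309 + 70 = 379. All match the printed table.

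**2. Can an on-schedule stool sample reach Days 149-253?** The SAP allows 3 days either side of a visit. As a generous assumption, add 3 days for the date of the first maintenance dose and 3 days for stool collection, 9 days in all.
- Week 26 sample: 99 ± 9 = Days 90-108
- Week 56 sample: 309 ± 9 = Days 300-318

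Neither reaches the Week 40 window. Only a PD sample, or one grossly off schedule, can.

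**3. What each analysis would contain at Week 40.**
- OC: essentially PD samples only.
- LOCF: a subject still in the study has no Week 40 sample and takes the latest value after maintenance Day 1, normally Week 26. Subjects with no such value stay missing. Some values labelled Week 26 are themselves PD samples, because that window opens at Day 2.
- MMRM, if run: a subject with a PD sample on Days 149-253 has left and gives no Week 56 sample. Essentially nobody is observed at both times, so the Week 40 by Week 56 term of the unstructured covariance has essentially no data. This follows from the schedule, whatever the dropout rate.

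**4. Size.** The documents give no dropout rate.
- If 2% to 20% of subjects with a Week 40 LOCF value had a PD sample in the window, the carried-forward share is 1 - 0.02 = 98% down to 1 - 0.20 = 80%.
- As an illustration of counts, assume 450 re-randomised, dropout spread evenly over Days 2-309 (308 days) and a stool sample at every PD visit. The window is 253 - 149 + 1 = 105 days. Expected PD samples = 450 x dropout x 105/308, which is about 15, 31 or 46 at 10%, 20% or 30% dropout. The primary population, Week 12 CR-70 responders, would be smaller.

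**5. Windows for the two sampled visits.** The same midpoint rule gives (99 + 309)/2 = 204, so Week 26 is Days 2-204 and Week 56 is Days 205-379. PD samples now labelled Week 40 would split: Days 149-204 (56 days) to Week 26 and Days 205-253 (49 days) to Week 56.

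**6. Side effects of the new windows.**
- A subject with a Day 99 sample and a PD sample on Days 149-204 has two values in one window. The closest-visit rule keeps Day 99. If LOCF works on windowed values, the PD value is lost from Week 56, whereas Table 4 now retains it. This concerns 56/105 = 53% of the window under even dropout.
- The Week 56 composites already mix windows: hs-CRP 254-379 (Table 4), CDAI 282-379 (Table 3), SES-CD 2-379 (Table 5). Opening calprotectin at Day 205 there would let a stool sample from study Week 12 + 204/7 = 41 count towards a Week 56 response.

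**The case against.** The strongest reply is that no Week 40 result is intended. The endpoint refers to scheduled visits, calprotectin's scheduled maintenance visits are Weeks 26 and 56/PD, and Table 4 only maps dates. That reading is possible, so it is not certain that a Week 40 p-value would be reported. But Table 4 names calprotectin, lists Week 40 as a scheduled week and says nothing to exclude it, and the Induction SAP shows that a separate table was the sponsor's own solution elsewhere. The text should settle the matter.

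Three stronger inferences are tempting, and the documents do not support them:
- *A PD sample on Days 205-253 is lost to Week 56.* Under LOCF, the primary method, it is carried into Week 56. It is absent from Week 56 only in OC and in the non-responder-imputed (NRI) binary analyses.
- *The MMRM will fail.* It is a sensitivity analysis used only where judged appropriate. A covariance term with essentially no data is a defect in the specification; non-convergence has not been shown.
- *LOCF simply repeats Week 26 for everyone else.* Some subjects have no value to carry, and some carried values come from early PD visits.

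The reply also stands on materiality: these endpoints are exploratory and non-ranked, with no multiplicity scheme. It stands too on the side effects in step 6: new windows alone, without rules for PD samples and composites, could discard values or change composite results.

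**Conclusion.** The point holds in limited form. Table 4 assigns calprotectin an analysis visit that the schedule does not support. Followed literally, it yields a Week 40 result that is either PD samples only (OC) or mostly carried-forward values (LOCF, 98% to 80% under the assumed 2% to 20% range). Any MMRM would include a time point with essentially no subjects also observed at Week 56.

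On-schedule Week 26 and Week 56 samples are placed correctly, so a reader should not infer that the Week 56 calprotectin endpoint is generally unsound. No ranked or confirmatory result is affected.

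The sampling schedule is taken from the text lists in the protocol and SAP, because the activity grids could not be read reliably by column. The size figures rest on assumed dropout; the structural finding does not.

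**What to change.** Before the maintenance analysis is run:
- Remove fecal calprotectin from Maintenance SAP Table 4 and give it its own table, as the Induction SAP does: Week 12, Day 1 or earlier; Week 26 (Day 99), Days 2-204; Week 56 (Day 309), Days 205-379.
- Report by-visit, OC, LOCF and MMRM calprotectin results at Weeks 26 and 56 only.
- State that LOCF to Week 56 uses the latest calprotectin value by date after maintenance Day 1, including a PD sample on Days 149-204 that was not selected for Week 26, so that none is lost.
- State which window calprotectin uses within the Week 56 composites. Keeping Days 254-379 there leaves their NRI results unchanged.

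The cost is one small table and two sentences, with no new data. One consequence to accept openly is that PD samples on Days 205-253 would enter the observed Week 56 calprotectin summary.
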